1. ABSTRACT

Atrial fibrillation (AF) is a common, morbid condition. Anticoagulation to prevent thromboembolic strokes is a foremost priority in AF but adherence is challenging for patients and lapses in anticoagulation are common. Chronic disease self-management (CDSM) is a recognized program to enhance self-efficacy and improve adherence, quality of life, and patient-centered health outcomes. Rural patients with AF experience increased vulnerability to adverse outcomes due to geographic and social isolation, poor health care access, and limited health literacy. Study team will conduct a single-center parallel group randomized clinical trial to test the efficacy of a relational agent to improve patient-centered care in AF delivered by smartphone. The Principal Investigator and study team have used the agent - a computer character that simulates face-toface conversation using voice, hand gesture and gaze cues to provide education, monitoring and problem-solving - to improve health behaviors and outcomes in individuals with limited computer and health literacy. Here, the team will expand its successful 30-day relational agent pilot to develop a novel CDSM program for AF. This study will combine the relational agent with the AliveCor Kardia smartphone heart rate and rhythm monitor. The team will implement a 4-month CDSM curriculum and assess its sustainability at 8 and 12 months. The trial randomizes 264 patients with AF who are receiving anticoagulation for stroke prevention to (1) the relational agent and Kardia intervention, accompanied by provider alerts for prespecified results; or (2) the control, consisting of an AF educational session and a smartphone with a general health application (WebMD). Our aims are: (1) To assess the effect of the relational agent and Kardia intervention on anticoagulant adherence, as determined by the proportion of days covered (PDC), and selfreport. (2) To identify the effect of the intervention on health care utilization, hospitalizations, emergency visits, and AF-related procedures at 1-year follow up. (3) To determine the effect of the intervention on the patient-centered outcomes of quality of life and symptoms, as measured by the AF Effect on QualiTy of life (AFEQT) measure, specific to AF, and the general Patient-Reported Outcomes Measurement Information System-29 Profile at baseline, 4, 8 and 12 months. (4) To examine mechanisms for the effect of the intervention by symptom burden, AF classification, health literacy and intervention use. The trial will additionally follow the cohort through the study period for exploratory analyses of rurality and outcomes associated with AF. Expected Results: In this project we will evaluate a scalable patient-centered intervention to improve anticoagulation adherence, health care utilization and patient-centered outcomes in vulnerable rural individuals with chronic AF. If proven successful, this intervention can be broadly disseminated to improve the care of patients with AF.

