3.0 STUDY AIMS

3.1 Aim 1

To assess the effect of the relational agent/Kardia intervention on anticoagulant adherence. We will quantify adherence to anticoagulation with (a) proportion of days covered (PDC) obtained from pharmacy data, and (b) self-report, at 4, 8, and 12 months. Hypothesis: Intervention participants will have better anticoagulant adherence than control arm participants as measured by objective and self-reported assessments of adherence.

3.2 Aim 2

To identify the effect of the intervention on health care utilization (HCU). We will quantify 12month HCU for intervention administration. Hypothesis: Intervention participants will have lower HCU events compared to control arm participants.

3.3 Aim 3

To determine the effect of the intervention on HRQoL and symptoms. We will compare HRQoL and symptoms between the intervention and control arms at 4, 8, and 12 months with the AF Effect on QualiTy of life (AFEQT) instrument (specific to HRQoL in AF) and the Patient-Reported Outcomes Measurement Information System (PROMIS)-29 Profile. Hypothesis:

Intervention participants will have superior HRQoL and lower symptom burden compared to control arm participants at 4, 8, and 12 months.

3.4 Aim 4

To examine mechanisms for the effect of the intervention. We will determine how patientcentered baseline factors including sex, race, health literacy, AF classification (paroxysmal versus chronic), and symptom burden moderate the intervention effect, and how intervention engagement and use, change in symptom burden, and AF therapies mediate the intervention effect on our primary and secondary outcomes.

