analyses. We will analyze PDC as continuous (range 0-1, higher ratio indicating better adherence) and binary (optimally adherent if ≥0.8) variables. We will assess differences between the 2 study arms in PDC at 12 months with linear regression (for continuous PDC) or logistic regression (for binary PDC) adjusting for trial stratification factor (as suggested by Kahan and Morris³⁷). We will conduct our secondary assessments of adherence at 4 8, and 12 months similarly. We will categorize individuals scoring ≥ 2 on any of the 3 self-report adherence items (range 1-5, Voils et al.³⁸) as nonadherent. To assess whether the effect of the intervention changes over time, we will use linear (for continuous measures) or non-linear (for categorical measures) mixed-effect models with random intercepts with adherence measures modeled as a function of study arm, study visit and their interaction. We calculated the statistical power to detect a range of difference in PDC (our primary outcome) between the intervention and control arms. After accounting for 10% attrition through 12 months (consistent with our prior RCTs), we determined that a sample size of 119 in each study arm will enable us to detect a minimum difference in PDC between the two groups as small as 11.7% with 85% power (assuming a SD=30%). Our power calculations assume use of 2-sided tests with 0.05 significance level. With an additional, unexpected 10% attrition (n=106 per arm, to accommodate for relocation, loss-to- follow-up, institutionalization, or death), we will be able to detect a minimum difference in PDC as small as 12.4% (0.41 standardized mean difference) with 85% power. Both are considered small effect sizes per Cohen's guidelines.³⁹

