Statistical approach for Aim 2. We will compare HCU across trial arms in models that again account for trial stratification factor.³⁷ We will use the electronic health record (EHR) in concert with 4-, 8-, and 12-month self-report to catalog events (hospitalization, emergency room and ambulatory visits, medications, and procedures) and classify them as related to AF. We will determine person-year of follow-up as starting from the date of randomization to the 12-month visit. We will then classify HCU in aggregate and by item as count outcomes. We will use generalized estimating equations (GEE) negative binomial regression models (chosen instead of Poisson regression due to expected over-dispersion in the data). Similar approaches will be used to assess counts for each HCU component. Based on preliminary data from an outpatient registry of individuals with chronic AF, we expect there will be 42.0 events for every 100 person-years in the control arm of the trial.⁴⁰We estimate that we have 85% power to detect a minimum absolute reduction of 21 events per 100 person-years in the intervention group, assuming an equivalent number of events in the control group at 12 months with a sample size of 132 per arm. A 20% attrition in study participation (n=106 per arm) at 12 months will still allow us to detect a minimum of absolute reduction of 23 events per 100 person-years in the intervention group with 85% statistical power. As exploratory analyses, we will perform survival analyses to compare the time to event between the intervention and control arms for preselected outcomes: AF-related hospitalization, emergency visit, or procedure; myocardial infarction; heart failure; stroke; and allcause mortality. Participants will contribute 18 to 51 months of follow-up: those without the event of interest will be censored at the end of follow-up. We will examine the assumption of proportional hazards and use Cox regression models to estimate the hazards ratio for assigned treatment for each outcome.

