Statistical approach for Aim 4. Subgroup analyses will be performed to assess moderation of the intervention effect by baseline patient-centered factors: (1) sex; (2) race (white vs non-white); (2) health literacy, assessed using the Newest Vital Sign (NVS); (3) AF classification (paroxysmal vs permanent), (4) symptom burden, measured by the AFEQT; (5) anticoagulant type (warfarin or direct oral anticoagulant (**DOAC**)); (6) self-reported anticoagulant nonadherence (<2 or \geq 2); and (7) duration of anticoagulation (<1 or \geq 1 year). We will formally test for effect modification by creating a regression model for each outcome including the subgroup variable, the intervention assignment and the interaction between the subgroup variable and intervention and evaluating the significance of the interaction term. The false discovery rate⁴³ will be used to adjust for multiple comparisons. Causal mediation analyses will be used to determine the degree to which intermediate patient-level factors explain the intervention effect as potential mediators of the primary and secondary outcomes.⁴⁴⁻⁴⁶ We will estimate the direct and indirect effects of the intervention on outcomes accounting for (1) changes in symptom burden during follow-up, measured by the AFEQT: (2) introduction of new AF therapies over 12-month study participation (antiarrhythmic, cardioversion or electrophysiologic study); (3) relational agent and Kardia usage; and (4) EHR alerts. Instead of emphasizing p-values, we will focus on estimation of mediation effect sizes.

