6.2 Inclusion Criteria

- 1. Adult, age ≥21.
- 2. Diagnosis of AF, identified from the EHR and confirmed by either an ECG, Holter, or a clinical note.
- 3. Resides in a municipality defined as rural by the Center for Medicaid and Medicare Services Rural Health Clinics Program.
- 4. Prescribed use of warfarin or DOAC (formerly NOAC) for AF stroke prevention.
- 5. English-speaking well enough to participate in informed consent and this study.
- 6. No plans to relocate from the area within 12 months of enrollment.

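### Aim 2's aggregate utilization count mixes hospital and emergency use with care that the intervention may itself prompt, and its 85% power allows for little or no over-dispersion

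*Combined protocol and SAP*

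**What the plan says.** Section 5.0, under Aim 2, will use the electronic health record and participant self-report to "catalog events (hospitalization, emergency room and ambulatory visits, medications, and procedures) and classify them as related to AF". It continues: "We will then classify HCU in aggregate and by item as count outcomes". Each component gets a similar model. Section 3.2 gives the direction: "Intervention participants will have lower HCU events compared to control arm participants". For power, "we expect there will be 42.0 events for every 100 person-years in the control arm of the trial"; the plan claims 85% power for a reduction of 21 per 100 person-years with 132 per arm, and of 23 with 106 per arm. The model is negative binomial because over-dispersion is expected. No dispersion value is given.

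HCU is described differently elsewhere. The Abstract speaks of "health care utilization, hospitalizations, emergency visits, and AF-related procedures at 1-year follow up". Section 8.1.15 covers hospitalizations, outpatient visits, referrals and medication use. The follow-up schedule in Section 9 has emergency visits, hospitalizations and inpatient days.

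Under Aim 4, one mediator of the effect on primary and secondary outcomes is "introduction of new AF therapies over 12-month study participation (antiarrhythmic, cardioversion or electrophysiologic study". Section 10.1 describes record alerts to the care teams of intervention participants, and the risk assessment in Section 10.3 accepts that findings may change care.

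**The concern.** The aggregate gives a clinic visit, a medication event or a cardioversion the same weight as an admission, and all of them count against the intervention. Yet the intervention is built to bring symptoms and rhythm findings to clinicians in one arm only. If this leads to visits, new drugs or procedures, the aggregate can stay level or rise while hospital and emergency use falls. The hypothesis and power statement concern events overall, and nothing says which result governs if the aggregate and an item disagree.

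Two further problems follow. Cardioversion is a procedure, so it is an Aim 2 event as well as an Aim 4 mediator. A new antiarrhythmic is in the same position if drug starts are counted. Part of that mediation estimate would then be built in by definition. In addition, the power statement does not say which events the 42.0 counts, and it makes no visible allowance for the over-dispersion that motivates the model.

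**Working it through.** **Inputs from Section 5.0.** Control rate 0.42 per person-year; intervention rate 0.21 (132 per arm) or 0.42 − 0.23 = 0.19 (106 per arm). Two-sided 0.05 is stated under Aim 1 and assumed here. One year per person is assumed.

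**Formula.** Power = Φ(|ln(r1/r0)|/SE − 1.96), with SE² = [(1/r0 + k) + (1/r1 + k)]/n, where k is the negative binomial dispersion (0 = Poisson).

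**Step 1: the plan's own figure.**
- 132 per arm, k = 0: SE² = (2.381 + 4.762)/132 = 0.0541, SE = 0.233; 0.693/0.233 = 2.98; power 84.6%.
- 106 per arm, k = 0: SE² = (2.381 + 5.263)/106 = 0.0721, SE = 0.269; 0.793/0.269 = 2.95; power 84.0%.

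Other common Poisson forms (rate difference, null variance, square root) give about 86% to 87%. Solved for k in the rate-difference and null-variance forms, 85% is reached at a dispersion of no more than about 0.25. The stated power is therefore Poisson or close to it.

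**Step 2: add over-dispersion (k assumed), 42 v 21, 132 per arm.**
- k = 0.5: SE² = 8.143/132; power about 80%.
- k = 1: SE² = 9.143/132; power 75%.
- k = 2: SE² = 11.143/132; power about 66%.

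**Step 3: dilution.** Halve the 42 to 21, then add D unaffected events per person-year to both arms. D is an assumption; the documents give no rate for medications, ambulatory visits or procedures.

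| D | Rates | Ratio | Power, k = 0 | Power, k = 1 |
|---|---|---|---|---|
| 0.5 | 0.92 v 0.71 | 0.77 | 47% | 29% |
| 1 | 1.42 v 1.21 | 0.85 | 32% | 16% |
| 2 | 2.42 v 2.21 | 0.91 | 20% | 9% |
| 4 | 4.42 v 4.21 | 0.95 | 13% | 5% |

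**Step 4: offset.** Add prompted events to the intervention arm only. Ten per 100 person-years (assumed) give 42 v 31, a ratio of 0.74, with Poisson power of 31%. Twenty-one per 100 cancel the halving exactly (21 + 21 = 42).

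**Step 5: overlap with Aim 4.** Cardioversion is on the mediator list and falls under procedures on the Aim 2 list. For each participant who has one, the mediator adds one to the outcome whatever happens to admissions or emergency visits.

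**The case against.** The strongest reply is that the plan already analyzes each component, so a fall in hospital or emergency counts would be visible, and exploratory time-to-event models cover AF-related hospitalizations, emergency visits and procedures. HCU is secondary. The question can also be read as one about total utilization, in which case prompted care belongs in the total. Section 9 points to hospital and emergency use as the working core, and Table 1 appears to list new AF therapies with the covariates, apart from HCU events. Phones are returned at 4 months, so device-triggered alerts arise in only about a third of the 12-month count.

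Much of this stands. It limits the harm but does not settle which count tests the hypothesis, and Section 5.0 still lists procedures and medications as HCU events. The amounts in Steps 3 and 4 are assumed, and restricting to AF-related events would shrink them by an unknown amount.

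Three stronger readings are tempting, and the documents do not support them:
- A reader might infer that pharmacy fills are medication events, so that better adherence would itself raise the count. Section 9 collects fills to compute the proportion of days covered; no text makes them HCU events.
- A reader might infer from the criterion "Prescribed use of warfarin or DOAC (formerly NOAC) for AF stroke prevention" that everyone contributes at least one event. A prescription held at entry need not be an event after randomization.
- A reader might infer that the 42.0 is the wrong rate for this list. The cited registry paper's title concerns drivers of hospitalization, which is suggestive only; the plan does not say what the figure counts.

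**Conclusion.** The concern holds as a problem of definition on a secondary outcome. As written, the aggregate can mask a fall in hospital and emergency use, no item is designated to answer the hypothesis, the HCU lists differ between sections, and cardioversion sits on both sides of a mediation analysis. That new antiarrhythmics do so too depends on drug starts being counted.

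The size of any dilution or offset cannot be fixed from the documents. The ratio of 0.85 rests on one assumed unaffected event per person-year in both arms, and is an illustration rather than a forecast. The power finding is firmer: 85% corresponds to Poisson or nearly so, and falls to about 80%, 75% or 66% at assumed dispersions of 0.5, 1 or 2. The power arithmetic is not wrong on Poisson terms, but it does not match the reason given for the model.

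**What to change.** - Name hospitalizations plus emergency visits, from randomization to 12 months, as the count that tests Aim 2, and state whether it is all-cause or AF-related. Say how an elective admission for an AF procedure is counted; placing it under procedures keeps the overlap out.
- Keep ambulatory visits, medications (defined as new AF drug starts, not fills) and procedures as by-item counts with no predicted direction.
- Use the hospital-plus-emergency count as the HCU outcome whenever new AF therapies are the mediator.
- State which events the 42.0 counts, and restate power for the chosen count with an assumed dispersion and a range.

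This needs plan wording and a new calculation, but no new data, since hospital and emergency use is already abstracted at each follow-up. The cost is fewer events and a less favorable stated power. If the rate were 30 per 100 person-years (assumed), a halving gives SE² = (3.333 + 6.667)/132 = 0.0758, SE = 0.275, 0.693/0.275 = 2.52, and Poisson power of about 71%. AF-related procedures, which the Abstract names, would be reported beside the test rather than within it.

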Statistical approach for Aim 3. We estimate that patients randomized to our intervention will have a clinically relevant improvement in HRQoL as demonstrated by AFEQT global score at 4-months follow-up vs. control. Our demonstration cohort (N=31) had a mean increase in AFEQT global score of 12±16 (from 64±23 to 76±19) over 30 days (range 0-100, greater scores indicating superior HRQoL). We will use linear regression adjusted for trial stratification factors and the baseline score as per Harrell⁴¹ to evaluate the differences in AFEQT global and domain-specific scores between study arms at 4 months. We will similarly assess the effect of the intervention for

each of the 4 AFEQT domains and the 8 symptom and HRQoL domains measured by the PROMIS-29 at 4 months. Next, we will assess sustainability of the intervention effect at 8 and 12 months using linear mixed models. Our power calculations assume a 90% 4-month assessment completion rate (to accommodate for 10% attrition), 2-tailed α =0.05, and standard deviation of 17 (representing the upper limit of the 95% confidence interval for the SD and consistent with the data used to determine the minimum important difference⁴²). Based on these assumptions, we expect our sample size (119 per arm) will enable us to detect a minimum difference in AFEQT between the two study arms at 4 months of at least 6.3, corresponding to 0.37 SD, a small effect size.³⁹ A 20% sample size attrition (n=106 per arm) at 12 months will allow us to detect a difference in AFEQT of at least 0.41 SD.

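### The AFEQT detectable difference of 6.3 points (0.37 SD) is credited to 119 per arm but matches 132 per arm; at 119 per arm and 85% power it is about 6.6 points (0.39 SD)

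*Combined protocol and SAP*

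**What the plan says.** All of this is in the combined protocol and SAP, section 5.0, under the statistical approach for Aim 3.

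- **Planning SD.** The calculation uses a two-sided alpha of 0.05 and a "standard deviation of 17 (representing the upper limit of the 95% confidence interval for the SD". Which SD is meant is not named. The value is also described as "consistent with the data used to determine the minimum important difference".
- **Available data.** The only AFEQT results printed are from the demonstration cohort: "Our demonstration cohort (N=31) had a mean increase in AFEQT global score of 12±16 (from 64±23 to 76±19) over 30 days".
- **Planned test.** "We will use linear regression adjusted for trial stratification factors and the baseline score" is the method for the 4-month comparison.
- **Result.** After allowing for 10% attrition, "we expect our sample size (119 per arm) will enable us to detect a minimum difference in AFEQT" of 6.3 points, which the plan equates to 0.37 SD. The next sentence gives 0.41 SD at 12 months with 106 per arm (20% attrition).
- **Power.** None is stated in this paragraph. Aims 1 and 2, in the same section, use 85%.

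**The concern.** The detectable difference is the only statement of how sensitive the trial is for its lead quality-of-life outcome, and it is presented as already net of dropout. If the figure belongs to the full randomized sample, the attrition allowance has not been applied, and a reader will think the 4-month comparison is more sensitive than the stated inputs make it.

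A second matter sits beside it. The value 17 is offered as a cautious upper limit, but the text does not say which SD it limits or in whom. The SDs printed just above it (16, 19 and 23, in 31 people) are too large, in so small a sample, to have an upper limit of 17.

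**Working it through.** **Inputs.** SD 17; two-sided alpha 0.05; 119 and 106 per arm (Aim 3 paragraph); 132 per arm randomized (section 5.0, opening paragraph). Power of 85% is an assumption carried over from Aims 1 and 2.

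**Formula.** Detectable difference = SD × (z₀.₉₇₅ + z_power) × √(2/n). At 85% power the bracket is 1.960 + 1.036 = 2.996. At 80% it is 1.960 + 0.842 = 2.802.

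**Step 1: where the plan's figure comes from.**

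| n per arm | Power | In SD units | In points (SD 17) | t-based |
|---|---|---|---|---|
| 132 | 85% | 2.996 × √(2/132) = 0.369 | 6.27 | 6.29 (0.370 SD) |
| 119 | 85% | 2.996 × √(2/119) = 0.388 | 6.60 | 6.63 (0.390 SD) |
| 119 | 80% | 2.802 × √(2/119) = 0.363 | 6.17 | 6.20 (0.365 SD) |
| 106 | 85% | 2.996 × √(2/106) = 0.412 | 7.00 | 7.03 (0.413 SD) |
| 106 | 80% | 2.802 × √(2/106) = 0.385 | 6.54 | 6.57 (0.387 SD) |

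The printed 6.3 points and 0.37 SD are reproduced by 132 per arm at 85% power. Solving for n with a 6.3-point difference, SD 17 and 85% power gives 131 per arm. Power for 6.3 points at 119 per arm is 81.6% (81.3% by the t distribution).

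**Step 2: is 85% the right power to assume?** The companion figure of 0.41 SD at 106 per arm is reproduced at 85% (0.412) and not at 80% (0.385).

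Aim 1 gives a further check. It states 11.7 percentage points at 119 per arm with SD 30 and 85% power, and 11.7/30 = 0.39 SD. So the same section gives 0.39 SD for 119 per arm in Aim 1 and 0.37 SD for 119 per arm in Aim 3, while both aims give 0.41 SD for 106 per arm.

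**Step 3: a check that does not depend on power.** With a common formula, detectable differences scale with 1/√n. Going from 106 to 119 per arm should multiply the figure by √(106/119) = 0.944. Going from 106 to 132 should multiply it by √(106/132) = 0.896. The printed ratio is 0.37/0.41 = 0.902. Allowing for rounding, it lies between 0.365/0.415 = 0.880 and 0.375/0.405 = 0.926. That range contains 0.896 and excludes 0.944.

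**Step 4: the description of SD 17.** Upper 95% limit of an SD = s × √(df/χ²₀.₀₂₅,df). With N = 31 and df = 30 the multiplier is 1.337.

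- Change SD 16: 21.4 (20.7 to 22.1 for a true value anywhere from 15.5 to 16.5).
- Follow-up SD 19: 25.4.
- Baseline SD 23: 30.7.

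None is 17. The residual SD after baseline adjustment can be derived from the same three figures:

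- Correlation: r = (23² + 19² − 16²)/(2 × 23 × 19) = 634/874 = 0.725.
- Residual SD: 19 × √(1 − 0.725²) = 13.1.
- Upper limit: 17.5 with df 30 (17.9 with df 29). Rounding of the printed SDs moves the df 30 limit between 16.3 and 18.6.

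**Step 5: what each SD would imply at 119 per arm and 85% power.** SD 17 gives 6.6 points, the residual-SD limit of 17.5 to 17.9 gives 6.8 to 7.0, and the change-score limit of 21.4 gives 8.3.

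**The case against.** **Power is not stated for Aim 3, so perhaps 80% was meant.** This does not rescue the figure. At 80% and 119 per arm the result is 6.17 points (0.36 SD), and the paired 106-per-arm figure would be 0.385 SD rather than 0.41. The ratio check in step 3 needs no power at all. It does assume that the 4-month and 12-month figures share one formula; the paragraph gives no separate assumptions for the second.

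**Baseline adjustment will sharpen the test.** This is fair as a statement about the trial. If the residual SD is near the point estimate of 13.1, 119 per arm would detect about 5.1 points at 85% power, and power for 6.3 would be about 96%. So the true sensitivity may be better than printed. That does not make 6.3 the result of the inputs the plan gives for it.

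**The stronger reading of SD 17.** A reader might infer that 17 is an arithmetic error, that the SD must be 21.4, and hence that the detectable difference is 8.3 points and power for 6.3 only about 62%. The documents do not support that:

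- They do not say that the interval is for the change-score SD, or that it comes from the 31-person cohort.
- The planned test adjusts for baseline, which makes the residual SD the relevant one. Its implied upper limit is compatible with 17 once rounding of the printed SDs is allowed for.
- They give a second basis for 17, the minimum-important-difference data, which cannot be checked here.

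What stands is narrower: the description matches no printed SD, and the text mentions no residual SD, correlation or derivation that would let a reader reach 17.

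**Conclusion.** The AFEQT figure does not follow from its own stated inputs. With SD 17 and 119 per arm, the detectable difference at 85% power is about 6.6 points (0.39 SD), not 6.3 (0.37 SD). The printed figure fits 132 per arm with no attrition. The gap is about 0.3 points, or equivalently power of about 81% instead of 85% for a 6.3-point difference.

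This rests on 85% power being intended for Aim 3, which the 106-per-arm figure supports, and on the usual two-sample comparison of approximately normal scores.

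On the SD, the conclusion is only that its source is unclear. An error in 17 is not shown, and 21.4 should not be imposed. The residual-SD calculation also assumes that the three printed SDs come from the same 31 people.

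The consequence is modest. AFEQT is a secondary outcome, and the trial's sample size does not depend on this figure.

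**What to change.** 1. Replace 6.3 points (0.37 SD) with about 6.6 points (0.39 SD) for 119 per arm at 85% power, or keep 6.3 and attribute it to 132 per arm without attrition.
2. State the power in the Aim 3 paragraph.
3. Say which SD and which sample the upper limit of 17 refers to, and show the derivation; otherwise drop the upper-limit description and rest 17 on the other stated source. If a residual SD was meant, give the correlation used; if its limit is taken as 17.5 to 17.9, the detectable difference at 119 per arm becomes 6.8 to 7.0 points. If the change-score SD was meant, restate the difference as about 8.3 points at 119 per arm.

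The cost is wording and one recalculated figure. The stated sensitivity becomes slightly less favourable; no participants, visits or analyses change.

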Race and sex. We will ensure our study cohort is 50% women and 30% non-white race, of whom 80% (24% overall) will be black race. (1) We have reviewed⁴⁷ AF is less prevalent in blacks⁴⁸⁻⁵⁰ but associated with worse outcomes⁵⁴ (2) Women have worse HRQoL and increased stroke risk than men.⁵¹⁻⁵³ (3) We have developed strategies to oversample participants of black race and female sex. Although the current trial is not specifically design to assess racial/sex variability in the intervention effect, since the overall effect has not yet been established, subgroups analyses among all race/sex groups will set the stage for further studies that focus on racial/sex effects. We note our statistical power for such trial participation: (1) if we randomize 64 study participants of black race, then we will have 85% power to detect a 22.8% PDC difference between trial arms. (2) Similarly, if we randomize 135 women, 51% of trial participants, then we will have 85% power to detect a 15.6% difference between trial arms.

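### Aim 3 states no power, and its 6.3-point (0.37 SD) detectable AFEQT difference at 119 per arm matches 132 per arm at the 85% power used elsewhere; at 119 it is 6.6 points (0.39 SD)

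*Combined protocol and SAP*

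**What the plan says.** All the relevant text is in section 5.0 of the combined protocol and SAP.

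- **Aim 3, assumptions.** "Our power calculations assume a 90% 4-month assessment completion rate (to accommodate for 10% attrition"), with "2-tailed α =0.05, and standard deviation of 17". No power level is given.
- **Aim 3, 4 months, 119 per arm.** The sample will "detect a minimum difference in AFEQT between the two study arms at 4 months of at least 6.3, corresponding to 0.37 SD".
- **Aim 3, 12 months, 20% attrition.** The next sentence says: ("n=106 per arm) at 12 months will allow us to detect a difference in AFEQT of at least 0.41 SD".
- **Aim 1, 119 per arm.** The detectable PDC difference is "as small as 11.7% with 85% power (assuming a SD=30"%).
- **Aim 1, 106 per arm.** The figure is "12.4% (0.41 standardized mean difference) with 85% power".
- **Race and sex.** With 64 Black participants, "we will have 85% power to detect a 22.8% PDC difference between trial arms". With 135 women the figure is 15.6%, also at 85%.

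Aim 2 also uses 85%. Aim 4 gives no power figure. The opening of section 5.0 gives 132 randomized per arm.

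**The concern.** Aims 1 and 3 use the same number per arm (119) and the same two-sided alpha. The standardized detectable difference should therefore be the same at the same power, whatever the outcome's SD. Aim 1 implies 11.7/30 = 0.39 SD, whereas Aim 3 prints 0.37 SD. At 106 per arm the two aims agree on 0.41 SD, and Aim 1 labels that figure 85% power. So the mismatch appears only at 119.

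Because Aim 3 gives no power, a reader cannot tell what power the main quality-of-life comparison was planned with. Someone who carries over the 85% used elsewhere in the section would take the stated difference to be better powered than it is.

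**Working it through.** **Inputs (section 5.0).** Two-sided alpha 0.05; AFEQT SD 17; PDC SD 30%; 132 randomized per arm. Attrition of 10% gives 132 × 0.9 = 118.8, or 119 per arm. Attrition of 20% gives 132 × 0.8 = 105.6, or 106 per arm. Power is 85% where the plan states it.

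**Formula.** For two means with n per arm, the normal approximation to the standardized detectable difference is d = (z₀.₉₇₅ + z_power) × √(2/n). At 85% power the bracket is 1.960 + 1.036 = 2.996. The two-sample t calculation gives slightly larger values and is the one that matches the plan's printed figures.

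**Step 1: reproduce the plan's other figures (t-test, 85% power, SD 30%).**

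| Case | Computed | Printed |
|---|---|---|
| 119 per arm | 11.70% | 11.7% |
| 106 per arm | 12.40% (0.41 SD) | 12.4% (0.41 SD) |
| 64 participants (32 per arm) | 22.8% | 22.8% |
| 135 participants (67.5 per arm) | 15.6% | 15.6% |

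All four agree, so this is evidently the method used.

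**Step 2: apply it to AFEQT (SD 17, 85% power).**

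| n per arm | d, normal | d, t | Points, t (17 × d) |
|---|---|---|---|
| 132 | 0.369 | 0.370 | 6.29 |
| 119 | 0.389 | 0.390 | 6.63 |
| 106 | 0.412 | 0.414 | 7.03 |

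The printed 6.3 points (0.37 SD) is the 132-per-arm row. Working backwards, 6.3/17 = 0.3706 at 85% power needs 131.7 per arm. Allowing 6.3 to be anything from 6.25 to 6.35 gives 133.8 down to 129.7, which does not reach 119.

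**Step 3: power of the printed difference.** At 119 per arm, 6.3/17 has power 0.8125 (t) or 0.8156 (normal), about 81%.

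**Step 4: can one power level give both Aim 3 figures?** Allowing for rounding:

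- 0.37 SD (0.365 to 0.375) at 119 per arm implies 80.1% to 82.1% power.
- 0.41 SD (0.405 to 0.415) at 106 per arm implies 83.5% to 85.3% power.

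The ranges do not overlap.

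**Step 5: other settings at 119 per arm.**

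- 80% power gives 6.20 points (0.36 SD), and 0.387 SD at 106 per arm.
- 90% power gives 7.17 points.
- One-sided alpha (normal approximation) gives 5.91 points at 85% power and 6.45 at 90%.
- A smaller SD changes the points but not d: an SD of 16.2 gives 6.3 points, but that is 0.39 SD.

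None of these yields 6.3 points together with 0.37 SD.

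**The case against.** The strongest reply is that Aim 3 never claims 85%. It lists its own assumptions, and on those 119 per arm does detect 6.3 points with about 81% power, above the common 80%. That is true, and it is why the conclusion about 6.6 points is conditional on 85%. It does not rescue the paragraph: an 80% target would have printed 6.2 (0.36 SD), and the 0.41 SD in the next sentence needs about 85%.

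A second reply is that the two Aim 3 figures concern different analyses: baseline-adjusted regression at 4 months and mixed models for 8 and 12 months. If 17 is a raw SD, which the plan does not say, baseline adjustment could account for 6.3. The correlation required is √(1 − (6.3/6.63)²) ≈ 0.31. That the printed effect size equals 6.3/17 does not exclude this, since an adjusted detectable difference divided by a raw SD would give the same ratio. But no correlation is stated, and the same correlation would give 0.414 × √(1 − 0.31²) ≈ 0.39 SD at 106 per arm, not 0.41. A different 12-month correlation is possible but nowhere mentioned.

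It is also fair to say that an omitted attrition step is an inference about where 6.3 came from. The mismatch itself does not depend on that inference. The point that the effect is small stands in full.

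**Conclusion.** The concern holds, as a minor correction. Aim 3 gives no power level. With a two-sample t-test, two-sided alpha 0.05 and SD 17, 119 per arm detects 6.6 points (0.39 SD) at 85% power, against the printed 6.3 (0.37 SD): a gap of 0.3 points or 0.02 SD. Equivalently, power for the printed difference is about 81%, roughly 4 percentage points below 85%.

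The 6.6 figure rests on 85% being the intended power, which Aim 3 does not say but which every power figure stated in section 5.0 supports. The internal inconsistency does not need that assumption: under the stated inputs, no single power level yields both Aim 3 figures.

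This is a planning figure for a secondary outcome and not evidence of an underpowered design. The check gives no credit for the planned baseline adjustment; a baseline correlation of about 0.31 or more, with 17 as a raw SD, would make 6.3 detectable at 119 per arm with 85% power.

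**What to change.** In section 5.0, Statistical approach for Aim 3, state the power and make the figure agree with it, in one of these ways:

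1. Give the detectable difference at 119 per arm as 6.6 points, 0.39 SD, with 85% power. This matches Aim 1 and the 0.41 SD already printed for 106 per arm.
2. Keep 6.3 points, 0.37 SD, at 119 per arm and state the power as about 81%, labelling the 0.41 SD at 106 per arm separately as 85%.
3. If 6.3 was meant to include the gain from baseline adjustment, say so, state that 17 is the raw SD, and give the correlation assumed at each time point.

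The cost is one figure and one phrase. Sample size, analysis and conduct do not change. Under the first option the stated detectable difference becomes slightly less favourable.
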